### 7.3 LOST TO FOLLOW-UP

A participant will be considered lost to follow-up if he or she fails to return for 2 scheduled clinic visits and is unable to be contacted by the study site staff.

The following actions must be taken if a participant fails to return to the clinic for a required study visit:

- The site will attempt to contact the participant and reschedule the missed visit within 2 weeks and counsel the participant on the importance of maintaining the assigned visit schedule and ascertain if the participant wishes to and/or should continue in the study.
- Before a participant is deemed lost to follow-up, the investigator or designee will make every effort to regain contact with the participant (where possible, 3 telephone calls and, if necessary, a certified letter to the participant's last known mailing address or local equivalent methods). These contact attempts should be documented in the participant's medical record or study file.
- Should the participant continue to be unreachable, he or she will be considered to have withdrawn from the study with a primary reason of lost to follow-up.

## 8 STUDY ASSESSMENTS AND PROCEDURES

### 8.1 EFFICACY ASSESSMENTS

See primary outcome.

### 8.2 SAFETY AND OTHER ASSESSMENTS

Study Measurements

Baseline demographics/comorbidities	Description
Age	At time of randomization, in years
Duration of type 1 diabetes	Based on self-report or extraction from medical record, in years
Type of insulin regimen	Generally, as two categories, NPH + regular (basal/bolus regimen) or premixed 70/30
Number of units of insulin per day	Total number of international units of insulin used per day, including all basal and bolus insulins.
Mean HbA1c (%) [SD]	HbA1c laboratory result (units=%), most recent
Complications of Type 1 Diabetes	Clinical presence or absence of diabetic retinopathy, neuropathy, or nephropathy (extracted from medical record)

Hypoglycemic events	Number of episodes of symptomatic hypoglycemic events in the past 12 months
Co-Primary Outcomes:	
Time-in-serious hypoglycemia	% spent less than 54mg/dl, averaged across all daily measures averaged across two CGM sensors starting 6 months after randomization
Time-in-range (TIR)	% between 70 and 180mg/dl inclusive, averaged across two CGM sensors 6 months after randomization
Secondary Outcomes:	
Time-in-hypoglycemia	% spent less than 70mg/dl
Time-above-range	% spent greater than 180mg/dl
Nocturnal hypoglycemic events	Number of events (defined as >=15mins in duration < 70mg/dl) between 1200 and 0600
Glycemic control (HbA1c)	Mean HbA1c lab result at baseline, 3, 6, 9 and 12 months after randomization
Rate of severe hypoglycemic events	Events requiring the assistance of an external third party person
Rate of diabetic ketoacidosis (DKA)	Measured by self-report and confirmed through review of hospital records
Quality of Life (e.g. Fear of Hypoglycemia Survey)	As assessed using validated instruments (PedsQL and Insulin Treatment Satisfaction Questionnaire (ITSQ)).
Adverse Events	
Hypoglycemic events (clinically significant events)	See primary and secondary outcomes above. Insulin in any form is known to be associated with low blood sugars. Therefore, we are measuring this as a primary/secondary outcome...but it also may be considered an adverse event/safety event.
Severe hypoglycemic events (<54mg/dl by CGM) > 10%	In the case severe hypoglycemia exceeds 10% on any CGM sensor, the treating clinician will be notified.
Skin discomfort/irritation	Self-report
Skin infection	Self-report
Mortality	All-cause mortality, assessed by 3 rd -party voluntary report to study staff and/or during failed attempts to follow-up with a trial participant

All other adverse events	Will be assessed periodically and categorized according to established procedures and taxonomy.
--------------------------	---

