## 2.3 RISK/BENEFIT ASSESSMENT

### 2.3.1 KNOWN POTENTIAL RISKS

Discomfort, skin rash/infection, inconvenience, or stigma of wearing a CGM sensor

Low blood sugar, high blood sugar, diabetic ketoacidosis, all due to change in insulin regimen

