Secondary outcomes will include: Time-in-hypoglycemia (<70mg/dl), time-above-range (either >180mg/dl or >250mg/dl), and number nocturnal hypoglycemic events (1200-0600h). We will also measure and compare overall glycemic control (HbA1c), the rate of severe hypoglycemic events (requiring the external assistance of another party), and the rate of symptomatic hypoglycemic events reported by clinical history, rate of diabetic ketoacidosis (measured by self-report and confirmed through review of hospital records) and overall mortality (all cause death). We will also explore durability of treatment effects by comparing % time <54mg/dl during the final 2 weeks of the 1-year follow-up.

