### 8.3.4 TIME PERIOD AND FREQUENCY FOR EVENT ASSESSMENT AND FOLLOW-UP

The occurrence of an adverse event (AE) or serious adverse event (SAE) may come to the attention of study personnel during study visits and interviews of a study participant presenting for medical care, or upon review by a study monitor.

All AEs including local and systemic reactions not meeting the criteria for SAEs will be captured on the appropriate case report form (CRF). Information to be collected includes event description, time of onset, clinician's assessment of severity, relationship to study product (assessed only by those with the training and authority to make a diagnosis), and time of resolution/stabilization of the event. All AEs occurring while on study must be documented appropriately regardless of relationship. All AEs will be followed to adequate resolution.

Any medical condition that is present at the time that the participant is screened will be considered as baseline and not reported as an AE. However, if the study participant's baseline condition deteriorates at any time during the study, it may be recorded as an AE.

Changes in the severity of an AE will be documented to allow an assessment of the duration of the event at each level of severity to be performed. AEs characterized as intermittent require documentation of onset and duration of each episode.

The local trial coordinator or research assistant will record all reportable events with start dates occurring any time after informed consent is obtained until 7 (for non-serious AEs) or 30 days (for SAEs) after the last day of study participation. At each study visit, the investigator will inquire about the occurrence of AE/SAEs since the last visit. Events will be followed for outcome information until resolution or stabilization.

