#### 8.3.6 SERIOUS ADVERSE EVENT REPORTING

The study clinician will immediately report to the sponsor (University of Pittsburgh) any serious adverse event, whether or not considered study intervention related, including those listed in the protocol or investigator brochure and must include an assessment of whether there is a reasonable possibility that the study intervention caused the event. Study endpoints that are serious adverse events (e.g., all-cause mortality) must be reported in accordance with the protocol unless there is evidence suggesting a causal relationship between the study intervention and the event (e.g., death from anaphylaxis). In that case, the investigator must immediately report the event to the sponsor.

All serious adverse events (SAEs) will be followed until satisfactory resolution or until the site investigator deems the event to be chronic or the participant is stable. Other supporting documentation of the event may be requested by the Data Coordinating Center (DCC)/study sponsor and should be provided as soon as possible.

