#### 9.4.3 ANALYSIS OF THE SECONDARY ENDPOINT(S)

The secondary outcomes are: Time-in-hypoglycemia (<70mg/dl), time-above-range (either >180mg/dl or >250mg/dl), and number nocturnal hypoglycemic events (1200-0600h). We will also measure and compare overall glycemic control (HbA1c), the rate of severe hypoglycemic events (requiring the external assistance of another party), and the rate of symptomatic hypoglycemic events reported by clinical history, rate of diabetic ketoacidosis (measured by self-report and confirmed through review of hospital records) and overall mortality (all cause death).

We will also measure and compare quality of life using validated tools (PedsQL v3 and Insulin Treatment Satisfaction Questionnaire) at baseline and at 6 and 12 months after randomization. A minimum clinically important difference in QoL scores will be determined *a priori*. The primary treatment comparison for QoL will be made between the two treatment arms at 6 months after randomization.

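### As written, the DKA rate needs a self-report plus hospital-record confirmation, so fatal DKA and admissions known only through an SAE report go uncounted, and the comparison between arms can be biased.

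*Combined protocol and SAP*

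**What the plan says.** The DKA rate is a secondary outcome. The measurement table in section 8.2 defines it as "Measured by self-report and confirmed through review of hospital records". The text of section 3 and section 9.4.3 repeat this, the latter as "rate of diabetic ketoacidosis (measured by self-report and confirmed through review of hospital records"). Section 9.4.3 adds no estimator, no denominator and no handling of death.

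Mortality is a separate secondary outcome, all-cause only. Section 8.2 has staff learn of deaths through voluntary third-party reports or failed attempts at follow-up. It describes no step for assigning a cause.

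Section 2.3.1 names DKA as a risk of the trial: "Low blood sugar, high blood sugar, diabetic ketoacidosis, all due to change in insulin regimen".

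The safety sections run on a wider net. Section 8.3.4 requires that "All AEs occurring while on study must be documented appropriately regardless of relationship". It expects staff to learn of events at visits, when a participant seeks care, and from monitoring. Section 8.3.6 has the study clinician report to the sponsor "any serious adverse event, whether or not considered study intervention related". Death and inpatient hospitalization are both SAE criteria under section 8.3.2. Nothing links these data to the DKA outcome.

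**The concern.** The definition has two conditions joined by an and. A participant who dies in the episode cannot meet the first. A participant whose admission reached the site through an SAE report, but who did not mention it when asked, does not meet it either. The episodes most likely to be lost are therefore the worst ones, and the loss is not random with respect to the outcome.

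DKA is a named risk of changing regimen, and only the glargine arm has its basal insulin changed by randomization (section 6.1.2). The DKA comparison is thus part of the safety case for glargine. Two analysts with the same data could also reach different counts, depending on whether they follow the definition literally or add what the SAE listing shows. The published DKA rate could then disagree with the trial's own SAE table.

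**Working it through.** **Reading the definition against its neighbours.** Two other rows of the section 8.2 table help to fix its meaning.
- Diabetes duration may come from self-report or from the medical record. Where either source was enough, the table says so; for DKA it requires both.
- Mortality comes from third-party report. The table therefore distinguishes a participant's own report from someone else's, and DKA is given only the former.

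**Looking for a rule elsewhere that restores the event.**
- Section 9.4.4 (safety analyses) points back to the primary outcome.
- Section 8.3.8 (events of special interest) is marked not applicable.
- The section 8.2 table lists hypoglycemia both as an outcome and as an adverse event. It does not do this for DKA.
- The win-ratio analysis in section 9.4.2 ranks death worst, but on a scale built on time below 54 mg/dl. It does not put the DKA event back.

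**Size.** The plan states no DKA rate, case fatality or power for this outcome, so there is no figure to reproduce. The counts below are assumptions. Let D1 and D0 be the true episodes in the two arms, and f1 and f0 the shares that are fatal or otherwise not self-reported. With 1:1 allocation and 12 months of follow-up, the ratio of counts is close to the ratio of rates:

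recorded ratio = (D1/D0) × (1 − f1)/(1 − f0)

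Within one arm, the rate is understated by f: 5% to 20% for an assumed f of 0.05 to 0.20.

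| Assumed case | True episodes | Fatal | True ratio | Recorded counts | Recorded ratio |
|---|---|---|---|---|---|
| Same total, higher case fatality | 20 v 20 | 4 v 1 | 1.00 | 16 v 19 | 0.84 |
| Same non-fatal, more fatal | 23 v 20 | 4 v 1 | 1.15 | 19 v 19 | 1.00 |
| More of both | 26 v 20 | 4 v 1 | 1.30 | 22 v 19 | 1.16 |
| More DKA, same case fatality | 30 v 20 | 3 v 2 | 1.50 | 27 v 18 | 1.50 |

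Using person-years instead changes little. With 200 participants per arm and half a year contributed by each fatal case, the first row becomes (16/198)/(19/199.5) = 0.85 against a true (20/198)/(20/199.5) = 1.01. The third row becomes 1.17 against 1.31.

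**When the direction reverses.** A true ratio of 1 or more is recorded below 1 only if it is smaller than (1 − f0)/(1 − f1). For f1 = 0.20 and f0 = 0.05 that limit is 0.95/0.80 = 1.19. For f1 = 0.10 and f0 = 0.05 it is 0.95/0.90 = 1.06. When f1 = f0 the factor is 1 and there is no bias in the ratio, although both rates are too low.

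**After the change proposed below.** If every fatal episode is documented and counted, the first row returns to 20 v 20, a ratio of 1.00.

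**The case against.** The strongest reply is that the definition is a one-line table entry that does not say only. It does not exclude a parent's account, which self-report may well be meant to cover in a trial that enrols from age 7 with parental consent under 18. Nor does it exclude DKA found first in a hospital or SAE record, and an SAE learned at interview is in effect a self-report. This stands as far as intent goes: the zero count for a fatal case follows from a literal reading, not from an explicit exclusion. It does not remove the need to say which reading applies.

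The second reply is that the harm is not hidden. Deaths count under mortality, deaths and admissions are SAEs, the DSMB sees safety data every 6 months, and a positive trial under section 9.1 rests on the co-primary CGM outcomes. This also stands. It limits the problem to one secondary safety outcome. One qualification applies: section 8.3.6 treats SAEs that are also study endpoints separately, so the immediate-reporting route for a DKA admission is not entirely clear. The general recording duty in section 8.3.4 applies in any case.

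The third reply is that confirmation has a purpose. The trial is open-label, and making unconfirmed reports the main count would invite differential reporting. That is right, and the fix keeps confirmation. A self-reported episode whose hospital record cannot be retrieved is an ordinary cost of confirmation, with no stated link to severity.

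A reader might infer that the arm with more fatal DKA will show the lower DKA rate. The documents do not support this as a general statement. The table above shows that it needs similar total DKA and higher case fatality in that arm; other patterns give equal, attenuated or unbiased ratios.

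**Conclusion.** The concern holds as a matter of severity-linked under-ascertainment. Followed as written, the definition leaves out fatal DKA and admissions that were not self-reported, and no other section restores them as DKA events. The comparison between arms can be attenuated, or reversed when case fatality differs while total DKA is similar. The 0.84 example shows how large this could be under assumed counts; it is not a prediction. The result rests on two assumptions: that the definition is applied literally, and that the share of lost episodes differs between arms. If the share is the same, only the level of the rates is wrong. It would go too far to say that the trial conceals the harm, since the deaths remain in the mortality and SAE data and are lost only as DKA. The change should be made before analysis, but it does not touch the primary conclusions.

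**What to change.** In sections 3, 8.2 and 9.4.3:
- Let a DKA episode be identified from any source the trial already holds: participant or caregiver report, AE or SAE report, hospital record, or death report.
- Keep documented confirmation, by hospital record or SAE documentation, for the main comparison between arms.
- Count fatal DKA in both the DKA rate and mortality where the SAE, hospital or death information supports it.
- Report all episodes, including unconfirmed ones, as a sensitivity analysis, because the trial is open-label.

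The cost is a change of wording, a merge of the SAE data with the outcome form, and some judgement on cause of death, made without reference to arm where possible. Because deaths may come to notice only through voluntary report, some will have no usable cause; those stay in mortality alone. No treatment, visit or sample size changes.

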## 8.3 ADVERSE EVENTS AND SERIOUS ADVERSE EVENTS

### 8.3.1 DEFINITION OF ADVERSE EVENTS (AE)

Adverse event means any untoward medical occurrence associated with the use of an intervention in humans, whether or not considered intervention-related (21 CFR 312.32 (a)).

### 8.3.2 DEFINITION OF SERIOUS ADVERSE EVENTS (SAE)

An adverse event (AE) or suspected adverse reaction is considered "serious" if, in the view of either the investigator or sponsor, it results in any of the following outcomes: death, a life-threatening adverse event, inpatient hospitalization or prolongation of existing hospitalization, a persistent or significant incapacity or substantial disruption of the ability to conduct normal life functions, or a congenital anomaly/birth defect.

Important medical events that may not result in death, be life-threatening, or require hospitalization may be considered serious when, based upon appropriate medical judgment, they may jeopardize the participant and may require medical or surgical intervention to prevent one of the outcomes listed in this definition. Examples of such medical events include allergic bronchospasm requiring intensive treatment in an emergency room or at home, blood dyscrasias or convulsions that do not result in inpatient hospitalization, or the development of drug dependency or drug abuse.

### 8.3.3 CLASSIFICATION OF AN ADVERSE EVENT

#### 8.3.3.1 SEVERITY OF EVENT

For adverse events (AEs) not included in the protocol defined grading system, the following guidelines will be used to describe severity.

- **Mild** – Events require minimal or no treatment and do not interfere with the participant's daily activities.
- **Moderate** – Events result in a low level of inconvenience or concern with the therapeutic measures. Moderate events may cause some interference with functioning.
- **Severe** – Events interrupt a participant's usual daily activity and may require systemic drug therapy or other treatment. Severe events are usually potentially life-threatening or incapacitating. Of note, the term "severe" does not necessarily equate to "serious".

#### 8.3.3.2 RELATIONSHIP TO STUDY INTERVENTION

All adverse events (AEs) must have their relationship to study intervention assessed by the clinician who examines and evaluates the participant based on temporal relationship and his/her clinical judgment. The degree of certainty about causality will be graded using the categories below. In a clinical trial, the study product must always be suspect.

- **Definitely Related** – There is clear evidence to suggest a causal relationship, and other possible contributing factors can be ruled out. The clinical event, including an abnormal laboratory test result, occurs in a plausible time relationship to study intervention administration and cannot be explained by concurrent disease or other drugs or chemicals. The response to withdrawal of the study intervention (dechallenge) should be clinically plausible. The event must be pharmacologically or phenomenologically definitive, with use of a satisfactory rechallenge procedure if necessary.
- **Probably Related** – There is evidence to suggest a causal relationship, and the influence of other factors is unlikely. The clinical event, including an abnormal laboratory test result, occurs within a reasonable time after administration of the study intervention, is unlikely to be attributed to concurrent disease or other drugs or chemicals, and follows a clinically reasonable response on withdrawal (dechallenge). Rechallenge information is not required to fulfill this definition.
- **Potentially Related** – There is some evidence to suggest a causal relationship (e.g., the event occurred within a reasonable time after administration of the trial medication). However, other factors may have contributed to the event (e.g., the participant's clinical condition, other concomitant events). Although an AE may rate only as "possibly related" soon after discovery, it can be flagged as requiring more information and later be upgraded to "probably related" or "definitely related", as appropriate.
- **Unlikely to be related** – A clinical event, including an abnormal laboratory test result, whose temporal relationship to study intervention administration makes a causal relationship improbable (e.g., the event did not occur within a reasonable time after administration of the study intervention) and in which other drugs or chemicals or underlying disease provides plausible explanations (e.g., the participant's clinical condition, other concomitant treatments).
- **Not Related** – The AE is completely independent of study intervention administration, and/or evidence exists that the event is definitely related to another etiology. There must be an alternative, definitive etiology documented by the clinician.]

### 8.3.3.3 EXPECTEDNESS

The local site PI will be responsible for determining whether an adverse event (AE) is expected or unexpected. An AE will be considered unexpected if the nature, severity, or frequency of the event is not consistent with the risk information previously described for the study intervention.

### 8.3.4 TIME PERIOD AND FREQUENCY FOR EVENT ASSESSMENT AND FOLLOW-UP

The occurrence of an adverse event (AE) or serious adverse event (SAE) may come to the attention of study personnel during study visits and interviews of a study participant presenting for medical care, or upon review by a study monitor.

All AEs including local and systemic reactions not meeting the criteria for SAEs will be captured on the appropriate case report form (CRF). Information to be collected includes event description, time of onset, clinician's assessment of severity, relationship to study product (assessed only by those with the training and authority to make a diagnosis), and time of resolution/stabilization of the event. All AEs occurring while on study must be documented appropriately regardless of relationship. All AEs will be followed to adequate resolution.

Any medical condition that is present at the time that the participant is screened will be considered as baseline and not reported as an AE. However, if the study participant's baseline condition deteriorates at any time during the study, it may be recorded as an AE.

Changes in the severity of an AE will be documented to allow an assessment of the duration of the event at each level of severity to be performed. AEs characterized as intermittent require documentation of onset and duration of each episode.

The local trial coordinator or research assistant will record all reportable events with start dates occurring any time after informed consent is obtained until 7 (for non-serious AEs) or 30 days (for SAEs) after the last day of study participation. At each study visit, the investigator will inquire about the occurrence of AE/SAEs since the last visit. Events will be followed for outcome information until resolution or stabilization.

